3. GENERAL INFORMATION

Objective	To assess the visual outcomes and quality of vision of patients receiving the AcrySof® Vivity Intraocular lens (IOL), when implanted in eyes with high ocular axial length ($\geq 24.5\text{mm}$), after uneventful cataract surgery.
	The Vivity IOL provides good refractive and visual outcomes at 3 months in subjects with long axial lengths in both eyes when combined with advanced power calculation formulae and intraoperative aberrometry (ORA).
Test Article(s)	AcrySof® Vivity Intraocular lens
Control Article(s)	None.
Sample size	40 eyes of 20 subjects
Study Population	Subjects presenting for cataract surgery who are interested in reducing their dependence on spectacles at all distances, and who are appropriate candidates for extended depth of focus (EDOF) lens implantation.
Number of sites	One
Study Design	Prospective, non-randomized, single-arm study.
Masking	None
Variables	Primary: Binocular uncorrected visual acuities at distance (6m), intermediate (66cm), and near (40 cm), 3 months postoperatively. Secondary: 
Percentage of eyes with absolute prediction error $\leq 0.5\text{D}$ at 3 months postoperatively.Monocular and binocular best-distance-corrected visual acuities at distance (6m), intermediate (66 cm), and near (40 cm), 3 months postoperatively.

- Manifest refraction (residual spherical equivalent refraction, residual sphere, and residual astigmatism), 3-months postoperatively.
- Questionnaire for visual disturbance scores (QUVID).
- Patient satisfaction questionnaire scores (IOLSAT).
- Binocular distance corrected low contrast visual acuity (25% contrast) at distance (6m).

Duration / Follow-up Preoperative to 3 months postoperative

The study will be registered with clinicaltrials.gov.

The study will be conducted in compliance with the protocol, GCP and applicable regulatory requirements

5. INTRODUCTION

Previous studies have shown that the AcrySof® Vivity IOL (Alcon Vision, LLC, Fort Worth, Texas, USA) provides good visual outcomes for patients at distance, intermediate and near,² the overall satisfaction rate with the lens is high.² This study aims to report on visual outcomes and patient reported visual disturbances and spectacle independence of the Vivity IOL in eyes with high axial length undergoing cataract surgery. Currently, there is no data on the visual outcomes of the Vivity IOL in patients with ‘long eyes’ ($\geq 24.5\text{mm}$).

6. OBJECTIVE(S)

The objective is to assess the visual outcomes and quality of vision of patients receiving the AcrySof® Vivity Intraocular lens (IOL), when implanted in eyes with high ocular axial length ($\geq 24.5\text{mm}$), after uneventful cataract surgery.

7. SUBJECTS

7.1. *Subject Population*

Eligible test subjects will be presenting for cataract surgery who are interested in a reduced dependence on spectacles for near, intermediate, and distance vision, who have axial length $\geq 24.5\text{mm}$ in both eyes, and who are considered appropriate candidates for extended depth of focus (EDOF) lens implantation. Target refraction will be -0.25 D in all eyes.

A total of 40 eyes of 20 subjects at one site will be enrolled. Both eyes of a subject must be enrolled. Subjects must meet the inclusion criteria. Prior to enrollment, subjects will be provided information on the study and asked to sign a patient information and consent form to participate. The patient information and consent form will be approved by an appropriate ethics committee.

7.2. *Inclusion Criteria*

Subjects are eligible for the study if they meet the following criteria:

Note: Ocular criteria must be met in both eyes.

- Undergoing uncomplicated bilateral cataract surgery with IOL implantation.
- Gender: Males and Females.
- Age: 50 years or older.
- Willing and able to provide written informed consent for participation in the study.
- Willing and able to comply with scheduled visits and other study procedures.
- Motivated for greater degree of spectacle independence vs monofocal IOL.
- Axial length $\geq 24.5\text{mm}$ in both eyes.

- Planned cataract removal by femtosecond laser.

7.3. Exclusion Criteria

If any of the following exclusion criteria are applicable to the subject or either eye, the subject should not be enrolled in the study.

- Ocular comorbidity that might hamper postoperative visual acuity.
- Previous refractive surgery.
- Irregular corneal astigmatism.
- Evidence of keratoconus as per Pentacam.
- Expected post-op VA worse than 20/25 (Snellen).
- Refractive lens exchange.
- Difficulties comprehending written or spoken English language.
- Patients with physical or intellectual disability (e.g. Down's Syndrome, Parkinson's Disease; unable to fixate).
- Clinically significant or severe ocular surface disease that would affect study measurements based on the investigator's opinion.
- Axial length <24.5mm.
- Evidence of macular pathology as per optical coherence tomography examination.

The principal investigator reserves the right to declare a patient ineligible or non-evaluable based on medical evidence that indicates they are unsuitable for the trial.

Pregnancy has a known effect on the stability of refractions and visual acuity. As such, subjects who become pregnant during the study will not be discontinued but their data may be excluded from analyses of effectiveness.

8. STUDY DESIGN

8.1. Study Design

This study is a single-arm unmasked clinical evaluation study of binocular uncorrected visual acuity at distance (6m), intermediate (66cm) and near (40cm), when implanted in eyes with high ocular axial length (≥ 24.5 mm), after successful bilateral cataract surgery. Subjects will be assessed preoperatively, operatively, and at 1 day, 1 week, 1 month, and 3 months postoperatively. Clinical evaluations will include administration of a visual disturbance questionnaire (QUVID) and a satisfaction questionnaire (IOLSAT), as well as measurement of binocular and monocular visual acuities and manifest refraction.

The primary outcome measure will be the binocular uncorrected visual acuities at distance (6m), intermediate (66cm), and near (40cm), 3 months postoperatively.

Secondary outcome measures are as follows:

- Percentage of eyes with absolute prediction error $\leq 0.5D$ at 3 months postoperatively.
- Monocular and binocular best-distance-corrected visual acuities at distance (6m), intermediate (66 cm), and near (40 cm), 3 months postoperatively.
- Manifest refraction (residual spherical equivalent refraction, residual sphere, and residual astigmatism), 3-months postoperatively.
- Questionnaire for visual disturbance scores (QUVID).
- Patient satisfaction questionnaire scores (IOLSAT).
- Binocular distance corrected low contrast visual acuity (25% contrast) at distance (6m).

8.2. Methods Used to Minimize Bias

As a single-arm study there is no expected bias. Patient selection will be based on the patient's interest and the surgeon's opinion as to whether they are a suitable candidate for EDOF IOL implantation.

The measurement of visual acuity will be conducted in a systematic fashion to minimize bias. Individuals conducting visual acuity measures will be instructed to perform the same testing in the same fashion for all subjects, with the same level of encouragement to subjects. Questionnaire instructions will be provided to all patients in a similar manner.

All data collection will be completed through provided Case Report Forms (CRFs) or computer files generated by automated test equipment. All site personnel involved in the study will be trained in regard to conducting study-specific procedures.

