9.2.1. Preoperative

At the preoperative exam, subjects will be consented, qualified for the study (compared with inclusion/exclusion criteria), and assigned a study ID/subject number. Subject numbers will be assigned sequentially at each site in the order of enrollment. Pre-operative qualification should take place no more than 60 days prior to surgery.

A medical history will be taken and exams will include the tests described below:

- manifest refraction,
- visual acuity

In addition, all site-specific, routine, usual standard of care preoperative measures should be undertaken. Data obtained from examinations within 24 months of consent are acceptable.

Measurements should be made as described in section 9.3 below.

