9.5. Discontinued Subjects

Discontinued subjects are those who do not have an exit visit or who come into the office to be exited prior to the scheduled final study visit. Subjects may be discontinued from the study at any time if, in the opinion of the investigator, their continued participation in the study poses a risk to their health. The reasons for discontinuation include:

- a. Adverse event;
- b. Lost to follow-up;
- c. Subject decision unrelated to an adverse event;
- d. Protocol violation;
- e. Treatment failure;
- f. Other.

To ensure the safety of all subjects who discontinue prior to Visit 6, investigators should assess each subject and, if necessary, advise them of any therapies and/or medical procedures that might be needed to maintain their health. Any changes in medical health and/or use of concomitant medications should also be captured.

10. ANALYSIS PLAN***10.1. Analysis Data Sets***

All subjects who are enrolled in the study will be evaluated for safety. Efficacy analyses will be performed based on data from those eyes where uncomplicated cataract surgery with Vivity IOL implantation was completed.

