18.2. Patient Discontinuation

Each study patient may voluntarily discontinue the study at any time they choose. Study patients who cannot complete the study for administrative reasons (e.g., non-compliance, failure to meet visit schedule, etc.) will be discontinued from the study. Study patients discontinued during the enrollment phase (prior to surgery) of the study will be replaced.

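### Section 8.2 wrongly says a single-arm study has no expected bias: entry is partly discretionary, non-evaluable rulings are untimed, and eligible patients not enrolled go unrecorded

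*Combined protocol and SAP*

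**What the plan says.** Section 8.2 (Methods Used to Minimize Bias) opens with "As a single-arm study there is no expected bias" and continues: "Patient selection will be based on the patient's interest and the surgeon's opinion as to whether they are a suitable candidate", meaning a candidate for an EDOF lens. The rest of the section covers uniform acuity testing and encouragement, similar questionnaire instructions, case report forms or automated files, and staff training.

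Other sections govern who enters and who is analysed:

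- Sections 3 and 7.1 define the population as cataract patients who want less spectacle dependence and are thought appropriate for an EDOF lens. Section 7.2 adds motivation, age and axial length.
- Section 7.3 sets objective exclusions (Pentacam, OCT, previous refractive surgery). It also excludes anyone whose acuity after surgery is forecast to be worse than 20/25, without saying how the forecast is made.
- Section 7.3 also says: "The principal investigator reserves the right to declare a patient ineligible or non-evaluable based on medical evidence". The evidence must show unsuitability for the trial, but no time is set for the ruling.
- Section 9.2.1: "Subject numbers will be assigned sequentially at each site in the order of enrollment".
- Section 18.2: "Study patients discontinued during the enrollment phase (prior to surgery) of the study will be replaced".
- Section 10.1: "Efficacy analyses will be performed based on data from those eyes where uncomplicated cataract surgery with Vivity IOL implantation was completed".

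No section of the available text asks for consecutive enrolment, a screening log, or counts of and reasons for non-enrolment.

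**The concern.** The sentence claims a property that the design lacks. With one arm there is no allocation to go wrong, but selection into the study, unmasked assessment and removal from analysis after enrolment can all still distort a mean. With no comparator, nothing offsets such a distortion.

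The study hypothesis in Section 3 is that the lens gives good outcomes in long eyes, and the evidence will be descriptive acuities from 20 people at one unmasked site. If the people enrolled or kept in the analysis differ from other eligible candidates, the mean describes a group that the reader cannot identify. Because Section 8.2 expects no bias, its remaining measures deal with how acuity is measured and leave selection unaddressed.

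**Working it through.** **1. The plan's own precision figure.** Section 11 gives n = 20, SD = 0.1 logMAR and a two-sided 95% t-based interval.

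Half-width = t(0.975, 19) × SD / √n = 2.093 × 0.1 / √20 = 2.093 × 0.02236 = 0.0468, which rounds to the stated 0.05. The figure reproduces. It covers sampling error only.

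**2. Where discretion enters.**

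| Stage | Rule | Discretionary? | Recorded? |
|---|---|---|---|
| Objective eligibility | Axial length, age, Pentacam, OCT (7.2, 7.3) | No | Enrolled subjects only |
| Forecast acuity | Worse than 20/25 excluded (7.3) | Yes, no method given | No record of those excluded |
| EDOF suitability | Surgeon's opinion (7.1, 8.2) | Yes, no definition given | No record of those judged unsuitable |
| Before surgery | Discontinued subjects replaced (18.2) | Partly | No flow count required |
| After enrolment | Ineligible or non-evaluable ruling (7.3) | Yes, needs medical evidence | No timing rule |

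Sequential numbering in 9.2.1 orders people already enrolled; it does not make enrolment consecutive. On timing, Table 15.1 schedules monocular uncorrected distance acuity at 1 day, 1 week, 1 month and 3 months. The primary binocular acuities come only at 3 months, but a ruling made at any time after day 1 can already be informed by that subject's acuity.

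**3. Illustration of size. The inputs are assumptions and are not in the documents.** Suppose the surgeon enrols the best fraction q of eligible patients, on a judgement that has correlation ρ with achieved acuity.

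Shift in mean = ρ × i × SD, where i = φ(z)/q and z is the normal quantile of q.

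The intensities are i = 0.195 (q = 0.9), 0.350 (q = 0.8), 0.497 (q = 0.7) and 0.798 (q = 0.5). With SD = 0.1 logMAR:

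| q | ρ = 0.2 | ρ = 0.3 | ρ = 0.5 |
|---|---|---|---|
| 0.9 | 0.004 | 0.006 | 0.010 |
| 0.8 | 0.007 | 0.011 | 0.018 |
| 0.7 | 0.010 | 0.015 | 0.025 |
| 0.5 | 0.016 | 0.024 | 0.040 |

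At 0.02 logMAR per letter, the range 0.004 to 0.040 is 0.2 to 2.0 letters. Relative to the half-width it is 0.004/0.0468 = 9% to 0.040/0.0468 = 85%.

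**4. Effect on the interval.** From the noncentral t with 19 degrees of freedom, a shift of 0.01, 0.02 or 0.03 logMAR lowers the coverage of a nominal 95% interval, taken as a statement about all eligible patients, to about 93%, 86% or 75%.

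Nothing in the documents gives q or ρ, so the study cannot be placed in these tables.

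**The case against.** The strongest reply is that EDOF suitability and motivation are the declared population, so selecting on them limits generalisability and is not in itself bias. This stands in part. But suitability is undefined and those judged unsuitable are not counted, so a reader cannot tell whom the declared population contains. Exclusion after enrolment remains a route to bias even within it.

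Second, a reader might infer that the plan does nothing to limit bias. The documents do not support that. There are objective eligibility criteria, the investigator's ruling must rest on medical evidence, and 8.2 and 9.3.2 standardise testing and scoring. The restriction to uncomplicated surgery in 10.1 also matches the stated objective. The gap is narrower: discretion among otherwise eligible patients, and the timing of rulings.

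Third, a reader might infer that the mean will be too favourable by nearly the whole half-width. That is also unsupported. It describes only the most extreme cell of the illustration, and the model assumes that surgeons rank patients on expected acuity, whereas 8.2 speaks of EDOF suitability. Section 11 says qualifying patients are scarce (about 17% of the older population), which makes turning away half of them less plausible. An optimistic direction is an inference, suggested by the forecast-acuity exclusion, and is not shown.

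Fourth, a screening log gives the enrolled fraction but not the correlation, so it cannot size the bias. That is correct. Its value is in showing who was left out and why.

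Fifth, the study has no comparator or success threshold, so a small shift changes no prespecified decision. That limits the consequence but does not make the sentence true.

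**Conclusion.** The point holds in a limited form. The statement in 8.2 is incorrect for an unmasked, uncontrolled, single-site study, and it leaves two correctable gaps: no record of eligible patients who were not enrolled, and no timing rule for ineligible or non-evaluable rulings. The absence of a log and of consecutive enrolment rests on the available text; the removed pages appear to be title, agreement and contact pages.

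No magnitude can be assigned. The range of 0.004 to 0.040 logMAR depends wholly on assumed correlations of 0.2 to 0.5, enrolled fractions of 50% to 90%, and an SD of 0.1. It shows that selection could matter relative to the planned precision, not that it will. The change should be made because it is cheap, and because a log has to be kept during enrolment and cannot be reliably rebuilt afterwards.

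**What to change.** 1. In 8.2, replace the sentence with a statement that selection bias and unmasked-assessment bias are possible, and that the uniform testing described there addresses measurement bias only.
2. Approach consecutive patients who meet 7.1 to 7.3, including the EDOF suitability judgement, until 20 are enrolled. Keep and report a screening log with the reason for each non-enrolment, including patients judged unsuitable for an EDOF lens.
3. Make and document any ineligible or non-evaluable ruling before that subject's postoperative acuities are reviewed. A cut-off at 3 months is too late, because monocular acuities exist from day 1. Where an earlier ruling is not possible, report the primary acuities with and without the excluded subjects.
4. Word the conclusion as applying to patients selected as EDOF candidates.

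The cost is a one-site log, a short rewrite of 8.2 and a more cautious conclusion. Sample size, treatment and visits are unchanged.

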9. STUDY PROCEDURE

9.1. Informed Consent / Subject enrollment

No subject will be enrolled into the study who does not meet the inclusion/exclusion criteria and does not sign the current approved informed consent document. The original signed informed consent documents will be maintained by the investigator as a permanent part of the subject's medical records. A signed copy will be provided to the subject.

9.2. Visits and Examinations

Subjects will participate in seven study visits, one eye per visit for bilateral surgery. Visits will include an uptake visit, two operative visits, and 5 total postoperative visits (Visit numbers 1-6 below). The visit schedule, complete with window and associated

CRF forms, are displayed in Table 9.2-1. Details of each study visit, including testing to be conducted, are provided below.

Table 9.2-1. Visit Schedule

Visit Number	Visit Name	Visit Window	CRF Number
1	Preoperative	-60 to 0 days from surgery	1
2,2a	Operative	0 from surgery	2,2a
3,3a	1 Day Postoperative	1-2 days postoperative*	3,3a
4	1 Week Postoperative	7 (± 2) days postoperative**	4
5	1 Month Postoperative	30 (± 10) days postoperative**	5
6	3 Months Postoperative	90 (± 20) days postoperative**	6

* relative to the operative eye

** relative to the date the last eye is operated on

9.2.1. Preoperative

At the preoperative exam, subjects will be consented, qualified for the study (compared with inclusion/exclusion criteria), and assigned a study ID/subject number. Subject numbers will be assigned sequentially at each site in the order of enrollment. Pre-operative qualification should take place no more than 60 days prior to surgery.

A medical history will be taken and exams will include the tests described below:

- manifest refraction,
- visual acuity

In addition, all site-specific, routine, usual standard of care preoperative measures should be undertaken. Data obtained from examinations within 24 months of consent are acceptable.

Measurements should be made as described in section 9.3 below.

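### Does the 24-month allowance for earlier examinations in Section 9.2.1 let outdated macular and corneal scans decide eligibility?

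*Combined protocol and SAP*

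**What the plan says.** Two timing sentences stand in Section 9.2.1 (Preoperative). The first concerns qualification: "Pre-operative qualification should take place no more than 60 days prior to surgery". Table 9.2-1 gives the same window for Visit 1. The second closes the list of preoperative tests: "Data obtained from examinations within 24 months of consent are acceptable". Immediately before it comes the instruction "In addition, all site-specific, routine, usual standard of care preoperative measures should be undertaken". The only tests that 9.2.1 names are manifest refraction and visual acuity.

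Section 7.3 lists 11 exclusion criteria. Two name the scan that decides them: "Evidence of macular pathology as per optical coherence tomography examination" and "Evidence of keratoconus as per Pentacam". Neither scan appears in the methods of Section 9.3 or in the schedule in Table 15.1, and no section sets an age limit for either.

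The same list has broader criteria that depend on no scan, among them "Ocular comorbidity that might hamper postoperative visual acuity" and a forecast of postoperative acuity below 20/25. It ends with a discretionary clause: "The principal investigator reserves the right to declare a patient ineligible or non-evaluable based on medical evidence".

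**The concern.** The 24-month sentence has no stated scope. Because it follows the instruction on routine care, it naturally takes in any scan a clinic takes routinely, including the two that decide exclusions. The 60-day rule does not obviously prevent this: it dates the act of comparing the subject with the criteria, not the data used to do so. A subject could therefore be qualified on time with an OCT or Pentacam scan some two years old.

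At stake is attribution. The study has one arm, no control and no masking, and its primary outcome is binocular uncorrected acuity at 3 months. Section 10.1 admits to the efficacy set any eye with uncomplicated surgery and a Vivity lens. Macular or corneal disease that arose after an old scan and went unnoticed before surgery would be counted as lens performance.

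**Working it through.** **1. Do the two sentences conflict?** No. One limits when qualification takes place, the other how old the examination data may be. Both can be obeyed at once. What is missing is a statement of scope.

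**2. How old could a scan be?** Inputs: 24 months before consent (9.2.1); consent and qualification at the preoperative visit, up to 60 days before surgery (9.2.1, Table 9.2-1).

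- 24 × 365.25 / 12 = 730.5 days, about 730.
- 730 + 60 = 790 days, about 26 months.

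This holds for the surgery that anchors Visit 1, which Table 9.2-1 does not identify. If that is the first eye, the scan would be older still at the second operation. The figure is what the wording tolerates, not expected practice.

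**3. What would have to go wrong?** Three things in sequence: a change arises after the scan, it is missed at the preoperative examination, and it lowers the 3-month acuity. The second step faces several requirements that hold whatever the age of the scan:

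- comparison with all criteria at the preoperative visit, within 60 days of surgery (9.2.1);
- the site's usual preoperative work-up (9.2.1);
- routine tests and a basic eye examination at every study visit, of which Visit 1 is one (9.3);
- exclusion for comorbidity or poor expected acuity, judged without reference to a particular scan (7.3).

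**4. The plan's own precision.** Section 11 gives n = 20, SD 0.1 logMAR and a t-based two-sided 95% interval:

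- half-width = t(0.975; 19) × 0.1 / √20 = 0.0468, stated as 0.05. It reproduces.

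**5. Scale of a possible effect.** The documents give neither the number of subjects affected nor the acuity lost. As an assumption for scale only, take one of 20 subjects and a binocular loss of 0.1 to 0.3 logMAR:

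- 0.1 / 20 = 0.005; 0.3 / 20 = 0.015 logMAR.
- Against 0.05: 0.005 / 0.05 = 10%; 0.015 / 0.05 = 30%.

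To move the mean by a full half-width, the losses would have to sum to 20 × 0.05 = 1.0 logMAR. That is ten subjects at 0.1 each, or four at 0.3 each (three give 0.9, four give 1.2).

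**6. Direction.** Missed disease makes acuity worse. It would count against the hypothesis in Section 3 that the lens performs well, and could not produce a falsely favourable mean.

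**7. Does old data enter the primary outcome itself?** No. Table 15.1 schedules binocular acuity only at Visit 6, so no preoperative measurement forms part of it.

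**The case for a change.** The strongest case is that the protocol itself chose OCT and Pentacam as deciding evidence and should therefore say how recent that evidence must be. Neither scan is scheduled after surgery, so a poor result could not be traced to its cause from study data. Declaring the patient non-evaluable would then rest on the investigator's discretion, in an unmasked study, once the acuity is known. Settling eligibility beforehand is cleaner and needs only a sentence or two. Section 9.3 does not say that routine testing includes either scan.

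Much of this stands as description: the scope is unstated, and the documents do not say whether the scans are routine at the site. It does not show a gain from changing the plan. This is a single-site study, so inconsistent reading between sites cannot arise. Nothing in the documents indicates that 24 months is too long for either scan; taken at face value, the sentence is a permissive choice by the sponsor. The allowance reaches axial length, the defining inclusion criterion, just as much, so a rule for two scans alone would be selective. A tighter rule would also need an age limit that the documents give no basis for choosing, and might require scans to be repeated.

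**Conclusion.** No change is needed. Section 9.2.1 leaves unsaid which examinations the 24-month allowance covers, and the literal reading includes those that decide eligibility. This is a gap in detail that a competent investigator fills at the preoperative visit, where the subject must be judged fit against every criterion within 60 days of surgery.

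No effect on the results can be shown from the documents. The illustrative shift of 0.005 to 0.015 logMAR is at most 30% of the planned half-width, and its direction is unfavourable to the lens. That range rests on an assumed one affected subject in 20 and an assumed loss of 0.1 to 0.3 logMAR; the 790 days rests on counting from the surgery that anchors Visit 1. The judgement would be different if several subjects were affected: about four of 20 at the upper assumed loss would be needed before the mean moved by the whole half-width. Nothing in the plan suggests that. A sponsor revising 9.2.1 for other reasons could state the scope of the allowance, but the analysis does not depend on it.
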